7. ADVERSE EVENTS: LIST AND REPORTING REQUIREMENTS

Adverse event (AE) monitoring and reporting is a routine part of every clinical trial. The following list of reported and/or potential AEs (Section 7.1) and the characteristics of an observed AE (Section 7.2) will determine whether the event requires expedited reporting **in addition** to routine reporting

7.1 Expected Toxicities

The most common AEs considered related to abemaciclib were headache (14%), nausea (11%), diarrhea (8%), and vomiting (8%).

7.2 Adverse Event Characteristics

- **CTCAE term (AE description) and grade:** The descriptions and grading scales found in the revised NCI Common Terminology Criteria for Adverse Events (CTCAE) version 4.0 will be utilized for AE reporting. All appropriate treatment areas should have access to a copy of the CTCAE version 4.0. A copy of the CTCAE version 4.0 can be downloaded from the CTEP web site

http://ctep.cancer.gov/protocolDevelopment/electronic_applications/ctc.htm.

- **Attribution** of the AE:
 - Definite – The AE *is clearly related* to the study treatment.
 - Probable – The AE *is likely related* to the study treatment.
 - Possible – The AE *may be related* to the study treatment.
 - Unlikely – The AE *is doubtfully related* to the study treatment.
 - Unrelated – The AE *is clearly NOT related* to the study treatment.

7.3 Expedited Adverse Event Reporting

7.3.1 Investigators **must** report to the Overall PI any serious adverse event (SAE) that occurs after the initial dose of study treatment, during treatment, or within 30 days of the last dose of treatment on the local institutional SAE form.

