2.4 Correlative Studies Background

In this study, correlative scientific aims will be addressed by performing analysis of both archival patient specimens and specimens obtained during the course of the study. The overarching goal of these studies is to explore possible predictors of response to abemaciclib amongst RB-positive TNBC's. Furthermore, studies will seek evidence of a pharmacodynamic response to abemaciclib therapy (through a tumor biopsy obtained on study) to determine if this correlates with response to therapy.

The main candidate biomarker of tumor sensitivity to CDK4/6 inhibitors is the presence of intact, functional Rb [6]. At the time of screening patients for eligibility, therefore, we will perform immunohistochemistry to identify RB status on archival tumor tissue. Only patients that are RB-positive (greater than 50% of tumor cells staining positive) will be eligible for the study.

Other than RB, there are no validated biomarkers for predicting response/resistance to CDK4/6 inhibitors in breast cancer. Candidate markers of response include amplification of cyclin D1 and loss of the CDK4/6 inhibitor p16 [5], which are thought to render tumors more dependent on the CDK4/6 pathway. Conversely, possible predictors of resistance include amplification of cyclin E1/E2, overexpression of cyclin E, mutations in TP53, and heightened activity of phosphoinositide-dependent kinase 1. Finally, a failure of CDK4/6 inhibition to adequately achieve suppression of RB-phosphorylation, even in the presence of intact RB, is also predicted to be associated with a lack of response to therapy.

In this study, patients with biopsy-accessible disease will be required to undergo tumor biopsy prior to initiating therapy. In addition, patients will undergo a second biopsy after completion of 1 cycle (28 days) of abemaciclib therapy. Analysis of pre-treatment biopsies (or archival tissue when pre-treatment biopsies are not available) will be performed to determine correlations with the predictive biomarkers listed above (and others) and response. Comparison of RB phosphorylation between baseline and C2D1 biopsies will be used to seek evidence of pharmacodynamic effect and explore its association with response. We will also perform exploratory genomic studies (whole exome sequencing) on the tumor tissue, as well as studies on fresh tumor tissue obtained at baseline aimed at determining therapeutic combinations that enhance the effects of CDK4/6 inhibitors in TNBC.

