- 3.1.9 The patient has an Eastern Cooperative Oncology Group (ECOG) performance status 0-1 (ECOG scale provided as Appendix A)
- 3.1.10 Patients must have normal organ and marrow function as defined below:
- Absolute neutrophil count $\geq 1500/\text{mm}^3$
 - Platelets $\geq 100,000/\text{mm}^3$
 - Hemoglobin ≥ 8 g/dL
- Note:* Patients may receive erythrocyte transfusions to achieve this hemoglobin level at the discretion of the investigator. Initial treatment must not begin earlier than the day the after the erythrocyte infusion
- Total Bilirubin ≤ 1.5 x the upper limit of normal (ULN) or ≤ 2.0 x the upper limit of normal (ULN) in patients with documented Gilbert's syndrome.
 - Serum creatinine ≤ 1.5 mg/dL OR calculated GFR ≥ 60 mL/min
 - Alanine aminotransferase (ALT) and aspartate aminotransferase (AST) ≤ 3 times the upper limit of normal. For patients with documented liver metastases, AST/ALT ≤ 5.0 times the upper limit of normal.
- 3.1.11 Female subjects of childbearing potential must have a negative serum pregnancy test at screening. Women of childbearing potential are defined as those who have not been surgically sterilized and have had a menstrual period in the past year

- 3.1.12 The patient must be ≥ 18 years old
- 3.1.13 Capable of understanding and complying with the protocol and has signed the informed consent document.
- 3.1.14 Able to swallow study drug.
- 3.1.15 Sexually active patients (male and female) must use medically acceptable methods of contraception during the course of the study and for 3 months after completion of study treatment. If a woman becomes pregnant or suspects she is pregnant while participating in this study, she should inform her treating physician immediately. While on the study and for 3 months after final drug administration, women may not breast-feed.
- 3.1.16 Confirmed availability of formalin-fixed, paraffin-embedded (FFPE) tumor tissue
- 3.1.17 Patients with tumor that is felt to be accessible to biopsy must be willing to provide tissue from a newly obtained core biopsy of a tumor lesion at baseline. Biopsies will be obtained up to 1 week (7 days) prior to initiation of treatment on Cycle 1, Day 1. Patients who undergo an attempted research biopsy procedure for the purpose of this protocol, and in whom inadequate tissue is obtained, are not required to undergo a repeat biopsy in order to continue on protocol.

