4. REGISTRATION PROCEDURES

4.1 General Guidelines for DF/HCC Institutions

Institutions will register eligible participants in the Clinical Trials Management System (CTMS) OnCore. Registrations must occur prior to the initiation of protocol therapy. Any participant not registered to the protocol before protocol therapy begins will be considered ineligible and registration will be denied.

An investigator will confirm eligibility criteria and a member of the study team will complete the protocol-specific eligibility checklist.

Following registration, participants may begin protocol therapy. Issues that would cause treatment delays should be discussed with the overall Principal Investigator (PI). If a participant does not receive protocol therapy following registration, the participant's registration on the study must be canceled. Registration cancellations must be made in OnCore as soon as possible.

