7.5 Expedited Reporting to the Food and Drug Administration (FDA)

The Overall PI, as study sponsor, will be responsible for all communications with the FDA. The Overall PI will report to the FDA, regardless of the site of occurrence, any serious adverse event that meets the FDA's criteria for expedited reporting following the reporting requirements and timelines set by the FDA.

7.6 [REDACTED]

SAEs will be reported to [REDACTED] on a MedWatch form as soon as possible and no later than 24 hours of the Investigator and/or Institution receiving notification of any serious adverse event experienced by a patient participating in the study and receiving study drug. Fax SAEs to the local safety representative using the following [contact].

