9.7.1 Guidelines for Tissue Acquisition and Biopsies of Metastatic Lesions

9.7.1.1 Collection of Specimen(s)

Tissue specimens will be collected from recurrent or metastatic lesions using standard institutional procedures. The amount of tissue collected will follow the guidelines listed below. If a participant has more than one site of disease, only one site needs to be biopsied in order to go on to the study and the site is left to the discretion of the patient and their treating physician. Core biopsies are preferred over fine needle aspirates when both are technically feasible. However, fine needle aspirates are acceptable and may be used for the baseline tissue sample. Participants who undergo a research biopsy procedure for the purpose of this protocol, and in whom inadequate tissue is obtained, are still eligible and are not required to undergo a repeat biopsy in order to enter the study. Research biopsies can be waived, with PI approval, in participants who do not have easily accessible disease.

For the baseline biopsy, ideally five core biopsies will be obtained and processed as follows:

- First core will be placed in 10% neutral buffered formalin and then made into a formalin fixed paraffin embedded (FFPE) block.
- Second core will be frozen in OCT
- Third core will be placed in 10% neutral buffered formalin and then made into an FFPE block.**
- Fourth core will be frozen in OCT**
- Fifth core will be placed in DMEM

**If a biopsy yields less than five cores, the PI may opt to have the 3rd or 4th core placed in DMEM to send to the lab of [name]. This can be discussed with [name] in advance of the procedure.

For the C2 biopsy, ideally five core biopsies will be obtained and processed as follows:

- First core will be placed in 10% neutral buffered formalin and then made into a formalin fixed paraffin embedded (FFPE) block.
- Second core will be frozen in OCT
- Third core will be placed in 10% neutral buffered formalin and then made into an FFPE block.
- Fourth core will be frozen in OCT

- Fifth core will be frozen in OCT

Guidelines for biopsy from various metastatic sites can be found below.

Breast: A goal of 3-6 core biopsy specimens will be obtained using standard institutional guidelines for a diagnostic core biopsy of a breast mass.

Skin/chest wall: A goal of 3 x 4-mm punch biopsies will be obtained.

Lymph node: A goal of 3-6 core biopsy specimens will be obtained using an 18-gauge needle.

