9.7.1.3 Risks of Research Biopsy and Procedures for Minimizing Risk

Potential risks according to site are:

Breast (core biopsy):

- Likely: local discomfort and minor bleeding.
- Less likely: moderate or major bleeding, need for blood transfusion, hospitalization due to bleeding or other complications, infection, pneumothorax, damage to adjacent organs.

Skin/chest wall (punch biopsy):

- Likely: local discomfort and minor bleeding
- Less likely: moderate or major bleeding, or infection

Lymph node, liver, or bone (core needle biopsy):

- Likely: local discomfort and minor bleeding
- Less likely: moderate or major bleeding, need for blood transfusion, hospitalization due to bleeding or other complications, infection, damage to adjacent organs. Additional risks may be present if intravenous conscious sedation is required

Pleural fluid (thoracentesis):

- Likely: local discomfort and minor bleeding
- Less likely: moderate or major bleeding, need for blood transfusion, hospitalization due to bleeding or other complications, infection, pneumothorax, damage to adjacent organs

Ascites fluid (paracentesis):

- Likely: local discomfort and minor bleeding
- Less likely: moderate or major bleeding, need for blood transfusion, hospitalization due to bleeding or other complications, infection, bowel perforation or damage to adjacent organs. In order to minimize the risk of a biopsy, only qualified personnel will perform these procedures.

Prior to the procedure, the physician performing the procedure will discuss the risks with each study participant, answer any questions, and obtain separate procedure consent. Patients will be evaluated for comorbidities or concomitant medications that may increase the risk of potential complications. For biopsies of lesions that are not superficial and clearly palpable, imaging studies such as CT or ultrasound will be used to guide the biopsy in order to minimize the risk of damage to adjacent structures. After lymph node biopsies, patients will be observed a minimum of 2 hours (range 2-4 hours) after the procedure, or according to standard institutional guidelines. After liver biopsies, patients will be observed a minimum of 4 hours (range 4-6 hours) after the procedure, or according to standard institutional guidelines. Less than the goal quantity of tissue is accepted for each type of biopsy, and will be left to the clinical judgment of the physician performing the procedure.

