13.6 Reporting and Exclusions

13.6.1 Evaluation of toxicity

All participants will be evaluable for toxicity from the time of their first treatment.

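### Expedited SAE reporting and toxicity evaluability begin with dosing, so serious harms of the required pre-dose research biopsy fall outside them

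*Combined protocol and SAP*

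**What the plan says.** Three safety provisions are tied to dosing:

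- Section 7.3.1 sends to the Overall PI "any serious adverse event (SAE) that occurs after the initial dose of study treatment", and closes 30 days after the last dose.
- Section 7.6 (heading and recipient redacted) sets a 24-hour limit for a serious event "experienced by a patient participating in the study and receiving study drug".
- Section 13.6.1 states: "All participants will be evaluable for toxicity from the time of their first treatment".

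The research biopsy comes earlier. Section 2.4 says that "patients with biopsy-accessible disease will be required to undergo tumor biopsy prior to initiating therapy", and 3.1.17 fixes the timing: "Biopsies will be obtained up to 1 week (7 days) prior to initiation of treatment on Cycle 1, Day 1". The requirement is not universal. It applies to accessible tumor, and under 9.7.1.1 "Research biopsies can be waived, with PI approval, in participants who do not have easily accessible disease". A second biopsy follows at C2D1, after one cycle.

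Section 9.7.1.3 lists, among the less likely risks of breast, lymph node, liver and bone core biopsies, transfusion, infection, damage to adjacent organs and "hospitalization due to bleeding or other complications". Section 9.7.1.4 adds the risks of sedation.

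**The concern.** The baseline biopsy is a research procedure that the protocol imposes on patients with accessible disease, and the protocol itself names serious risks for it. The provisions that would bring a serious event promptly to the Overall PI, who under 7.5 is also the study sponsor and handles communication with the FDA, open only once drug has been given. Two identical complications of two biopsies in the same trial would be treated differently according to whether the first capsule had been taken, and the documents give no reason for the difference. What is at stake is oversight of a research-only risk, above all when the complication is bad enough that the patient never starts treatment.

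**Working it through.** No arithmetic applies. The check sets the provisions on a timeline and then asks of each other route whether it fills the gap.

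**Timeline.** Take a patient admitted to hospital for bleeding two days after a biopsy. I assume that admission makes the event serious, since the protocol text gives no SAE definition of its own.

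| | Baseline biopsy | C2D1 biopsy |
|---|---|---|
| When | Within 7 days before C1D1, pre-dose | After a 28-day cycle of drug |
| 7.3.1 SAE report to Overall PI | Outside, if the event precedes the first dose | Inside |
| 7.6 24-hour report | Outside, no drug yet received | Inside, for a patient still on drug |
| 13.6.1 toxicity evaluability | Outside | Inside |

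**Other routes for the baseline event.**

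1. *Section 7.7* requires Grade 2 or higher adverse events in routine submissions to the Overall PI. No start date is given, so a pre-dose event can be read as covered. The route is routine rather than expedited. It uses the toxicity forms, while 13.6.1 dates toxicity from first treatment.
2. *The Section 10 calendar* marks AE evaluation at Screening and at C1D1, and assessments precede dosing. This would detect the event, but it sets no duty to file an SAE report, and a patient who is never dosed may have no C1D1 visit.
3. *Sections 7.3.2 and 7.4* route events to the IRB office and to Risk Management under institutional policies. Neither text has a first-dose limit. The policies are not in the documents, so their reach cannot be checked, and neither route leads to the Overall PI.
4. *Section 7.5* has no first-dose limit either, but it describes what the Overall PI sends to the FDA. It does not say how the event reaches the Overall PI.
5. *Section 4.1* says that problems delaying treatment should be discussed with the Overall PI. For a registered patient this would often bring the event to light, as a discussion and not as an SAE report.
6. *Section 5.5* requires immediate notice to the Overall PI of unusual or life-threatening complications. It stands in the section on stopping protocol therapy, and an admission for a listed biopsy risk need be neither unusual nor life-threatening.
7. *Section 12.2* says DSMC information may include reported Grade 2 or higher unexpected events. A listed biopsy risk might not count as unexpected.

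**Attribution.** All five categories in 7.2 relate the event to study treatment. A biopsy injury before any drug has no category that fits it except one denying a relation to treatment, so even a recorded event would not be identifiable as procedure-related from that field.

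**Patients never dosed.** If the complication prevents dosing, 4.1 says that the patient's "registration on the study must be canceled", and 13.6.2 treats the patient as inevaluable and replaces them. The documents do not say whether safety forms are still completed. This chain assumes registration before the biopsy. The calendar puts the biopsy under Screening and 9.7.1.1 speaks of biopsy as a step to study entry. If the biopsy comes first, there is no registration to cancel, and the text is equally silent on reporting.

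**The case against.** The strongest reply is that this is a narrow gap in expedited reporting. Section 7.7 reaches the Overall PI and has no first-dose limit, AE evaluations are scheduled before dosing, the IRB, Risk Management and FDA routes are not restricted to dosed patients, and 4.1 expects treatment delays to be discussed with the Overall PI. Section 13.6.1 defines who contributes to drug toxicity, to which an undosed patient cannot contribute, and 13.6.2 concerns efficacy. Neither forbids recording a procedure event, and biopsy safety is not a trial objective.

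Most of this stands, and it limits the point. A reader might infer that serious baseline biopsy harms are not captured at all, or that no rule brings them to the Overall PI. The documents do not support that, for the reasons just given. A reader might also apply an assumed complication rate to the 38 planned patients to obtain a probability of a missed event. That would not be evidence: the rate would be invented, not every patient is biopsied, and the result would assume that every other route fails. The figure of 2 per 1000 in 9.7.1.4 comes from upper gastrointestinal endoscopy under sedation and does not supply the missing rate. Bowel perforation is listed only for paracentesis, not for core biopsy.

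What the reply does not answer is the difference between the two biopsies. None of the other routes clearly requires the report that 7.3.1 would require at C2D1.

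**Conclusion.** The point holds in a limited form. Serious harms of the pre-dose research biopsy fall outside 7.3.1, 7.6 and 13.6.1, while the same harms after the C2D1 biopsy fall inside. Other routes may bring them to light, but the start of 7.7 is undefined and no route clearly requires an expedited SAE report to the Overall PI. The gap is widest for patients whose complication prevents dosing.

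Its size in events cannot be stated. At planned accrual there are at most 38 scheduled baseline biopsies in treated patients, fewer where disease is inaccessible or the biopsy is waived, plus any in patients biopsied but never dosed. The conclusion rests on the wording of the windows and on no assumed rate. It is subject to institutional reporting policies that the documents do not reproduce. The response rate, decision rule, error rates and sample size are untouched. The change is worth making because it improves oversight of a research-only risk at very little cost.

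**What to change.** - In 7.3.1, and in 7.6 where it applies, start the SAE window at the first protocol-mandated research procedure. Until the first dose, limit it to events attributed to that procedure. After the first dose, leave it as written.
- State the same start for 7.7, so that it agrees with the AE evaluations in the calendar.
- Add attribution to study procedures to 7.2, alongside attribution to study treatment.
- State that procedure-related events in patients biopsied but never dosed are reported to the Overall PI and the DSMC, even though 4.1 and 13.6.2 cancel the registration and replace the patient.
- Leave 13.6.1 unchanged as the definition of drug-toxicity evaluability.

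The cost is protocol wording, an added attribution field and a few extra SAE forms, with a slightly higher reported event count. No visit, test or patient is added.

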7.3.2 DF/HCC Expedited Reporting Guidelines

Investigative sites within DF/HCC will report AEs directly to the DFCI Office for Human Research Studies (OHRS) per the DFCI IRB reporting policy.

7.4 Expedited Reporting to Hospital Risk Management

Participating investigators will report to their local Risk Management office any participant safety reports or sentinel events that require reporting according to institutional policy.

7.5 Expedited Reporting to the Food and Drug Administration (FDA)

The Overall PI, as study sponsor, will be responsible for all communications with the FDA. The Overall PI will report to the FDA, regardless of the site of occurrence, any serious adverse event that meets the FDA's criteria for expedited reporting following the reporting requirements and timelines set by the FDA.

7.6 [REDACTED]

SAEs will be reported to [REDACTED] on a MedWatch form as soon as possible and no later than 24 hours of the Investigator and/or Institution receiving notification of any serious adverse event experienced by a patient participating in the study and receiving study drug. Fax SAEs to the local safety representative using the following [contact].

7.7 Routine Adverse Event Reporting

All Grade 2 or higher Adverse Events **must** be reported in routine study data submissions to the Overall PI on the toxicity case report forms. **AEs reported through expedited processes (e.g., reported to the IRB, FDA, etc.) must also be reported in routine study data submissions.**

8. PHARMACEUTICAL AGENT INFORMATION

A list of the adverse events and potential risks associated with the investigational agent administered in this study can be found in Section 7.1.

